### **12.3 Sample Size/Accrual Rate**

Enrollment in cohorts A & B is expected to be 4 patients per month per cohort, with a total of 48 patients per cohort enrolled 1:1 between regorafenib: placebo. Enrollment is expected to be completed in 12 months with a minimum follow-up period of 6 months.

For cohort C, enrollment is expected to be 3 per month for a total enrollment of 30 patients over 10 months. (Enrollment for this cohort is complete.)

For cohort D, enrollment is expected to be 0.5 per month (1 each fusion positive, fusion negative types) for a total enrollment of 12 patients over 24 months.

For cohort E, enrollment is expected to be 0.5 per month (1 each fusion positive, fusion negative types) for a total enrollment of 12 patients over 24 months.

## **12.4 Stratification Factors**

Patients will be stratified by WHO performance status ([0 or 1] vs 2) and by number of prior lines of therapy (1 vs 2 or more). No more than 1/3 of patients will be permitted on cohorts A and B with WHO performance status 2.

## **12.5 Analysis of Secondary Endpoints**

Descriptive statistics will be generated for secondary endpoint variables.

Methodologies for variables that are proportions will include construction of confidence intervals for each group and for the difference between groups. For example, a Fisher exact test will be used for single-population analyses, while a Mantel-Haenszel test will be used for analyses combining data across strata.

Methodologies for time-to-event variables will include construction of 95% confidence intervals for each group separately and for the difference between groups. For analysis, a log-rank test will be used. Logistic regression and analysis of covariance methods on measured variables with baseline measures as covariables. Kaplan Meier curves will be displayed for time-to-event data.

## **13. ETHICAL AND LEGAL CONDUCT OF THE STUDY**

The procedures set out in this protocol, pertaining to the conduct, evaluation, and documentation of this study, are designed to ensure that the investigator abide by Good Clinical Practice (GCP) guidelines and under the guiding principles detailed in the Declaration of Helsinki. The study will also be carried out in keeping with applicable local law(s) and regulation(s).

Documented approval from appropriate IRBs will be obtained for all participating centers before start of the study, according to GCP, local laws, regulations and organizations. When necessary, an extension, amendment or renewal of the IRB approval must be obtained and also forwarded to SARC.

Strict adherence to all specifications laid down in this protocol is required for all aspects of study conduct; the investigator may not modify or alter the procedures described in this protocol.

Modifications to the study protocol will not be implemented by the investigator without discussion and agreement by SARC and the sponsor, Bayer. However, the investigator may implement a deviation from, or a change of, the protocol to eliminate an immediate hazard(s) to the trial subjects without prior IEC/IRB/SARC/Bayer approval/favorable opinion. As soon as possible, the implemented deviation or change, the reasons for it and if appropriate the proposed protocol amendment should be submitted to the IEC/IRB/head of medical institution. Any deviations from the protocol must be explained and documented by the investigator.

The Principal Investigator is responsible for the conduct of the clinical trial at the site in accordance with Title 21 of the Code of Federal Regulations and/or the Declaration of Helsinki. The Principal Investigator is responsible for personally overseeing the treatment of all study patients. The Principal Investigator must assure that all study site personnel, including sub-investigators and other study staff members, adhere to the study protocol and all FDA/GCP/NCI regulations and guidelines regarding clinical trials both during and after study completion.

The Principal Investigator at each institution or site will be responsible for assuring that all the required data will be collected and properly documented.

Subjects will not be paid to participate in this study.

### **13.1 Subject information and consent**

Each subject / legal representative or proxy consentor will have ample time and opportunity to ask questions and will be informed about the right to withdraw from the study at any time without any disadvantage and without having to provide reasons for this decision.

Only if the subject / legal representative or proxy consentor voluntarily agrees to sign the informed consent form and has done so, may he/she enter the study. Additionally, the investigator and other information provider (if any) will personally sign and date the form. The subject / legal representative or proxy consentor will receive a copy of the signed and dated form.

The signed informed consent statement will be uploaded into the database and will remain in the investigator site file or, if locally required, in the patient's note/file of the medical institution.

In the event that informed consent is obtained on the date that baseline study procedures are performed, the study record or subject's clinical record must clearly show that informed consent was obtained prior to these procedures.

1. If the patient is not capable of providing a signature, a verbal statement of consent can also be given in the presence of an impartial witness (independent of Bayer and the investigator). This is to be documented by a signature from the informing physician as well as by a signature from the witness.
2. For minors or adults under legal protection, consent shall be given by the legal guardian(s). The consent of a minor or adult under legal protection shall also be requested where such a person is able to express his/her own will. His/her refusal or the withdrawal of his/her consent may not be disregarded.
3. In emergency situations, when prior consent of the patient is not possible, the consent of the patient's legal representative(s) or proxy consentor, if present, should be requested. The patient should be informed about the study as soon as possible and his/her consent to continue

the study should be requested.

The informed consent form and any other written information provided to subjects / legal representatives or proxy consenters will be revised whenever important new information becomes available that may be relevant to the subject's consent, or there is an amendment to the protocol that necessitates a change to the content of the subject information and / or the written informed consent form. The investigator will inform the subject / legal representative or proxy consentor of changes in a timely manner and will ask the subject to confirm his/her participation in the study by signing the revised informed consent form. Any revised written informed consent form and written information must receive the IEC/IRB's approval / favorable opinion in advance of use.

### **13.2 Publication policy**

Timely publication is central to SARC's mission. A manuscript should be prepared and submitted for publication within one year of availability of the study results. Authorship will align with the SARC publication policy.

### **13.3 Confidentiality**

All records identifying the subject will be kept confidential and, to the extent permitted by the applicable laws and/or regulations, will not be made publicly available.

Should direct access to medical records require a waiver or authorization separate from the subject's statement of informed consent, it is the responsibility of the Investigator to obtain such permission in writing from the appropriate individual.

**APPENDIX A: Performance Status Criteria**

WHO Performance Status Scale	
Grade	Descriptions
0	Asymptomatic (Fully active, able to carry on all pre-disease activities without restriction)
1	Symptomatic but completely ambulatory (Restricted in physically strenuous activity but ambulatory and able to carry out work of a light or sedentary nature. For example, light housework, office work)
2	Symptomatic, <50% in bed during the day (Ambulatory and capable of all self-care but unable to carry out any work activities. Up and about more than 50% of waking hours)
3	Symptomatic, >50% in bed, but not bedbound (Capable of only limited self-care, confined to bed or chair 50% or more of waking hours)
4	Bedbound (Completely disabled. Cannot carry on any self-care. Totally confined to bed or chair)
5	Deceased

**Fax or email to the following within 24 hours of PI becoming aware of event:**

[[contact]](mailto:[contact]); [contact]

Study Title	SARC024: A blanket protocol to study oral regorafenib in patients with selected sarcoma subtypes
Site PI Name	
Patient Unique Study #	
Adverse Event (CTCAE v4.03)	
Adverse Event Grade	
Adverse Event Causality Relationship	 Yes  No
Type of Report (Check one)	 Initial  Follow-up
All serious adverse events will be reported and documented on Form FDA 3500 A (MedWatch Form) Please fax completed MedWatch Form along with this Fax Coversheet.	

**Completed by:** \_\_\_\_\_  
**Date:** \_\_\_\_\_

## **APPENDIX C. Study Drug Diary Template**

(See subsequent page)

## SARC024 Study Drug Diary

To be completed by the site: Patient ID: _____ Cycle number: _____ Cycle Start Date _____																				
Date																				
Study drug																				
Number of tablets taken*																				
Reason for missed dose																				
Watching for Side Effects																				
Blood pressure**																				
Nausea*** (see scale below)																				
Vomiting (number of times)																				
Diarrhea (number of times)																				
Watching for Other Side Effects																				
Other Medications																				

**ONLY TAKE STUDY DRUG FOR 3 WEEKS (21 DAYS). DO NOT TAKE ANY STUDY DRUG DURING WEEK 4 OF EACH CYCLE.**

\* If you are 8 hours or more late from your scheduled dose, do not take the dose, and please write "M" in the box.

\*\* Check blood pressure every week.

\*\*\* Rate nausea "1" if you are able to eat and drink a reasonable amount, "2" if you can eat and drink but the amount is decreased significantly, or "3" if you can't eat and drink.

Note: Try to take the study drug daily at the same time, if possible, and consistently with or without food. Do not retake if vomiting occurs.

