### 5.4 Study drug administration

Regorafenib (or placebo) is administered as monotherapy during the study. For adults on the study, the starting dose is 160 mg daily for 3 weeks on, 1 week off, taken in the morning with a low-fat meal each day.

The medication should be taken within 8 hours of the same time each day, otherwise should be marked as a missed dose. One cycle is 28 days.

For adults, four 40 mg regorafenib or placebo tablets should be taken in the morning with approximately 8 fluid ounces (240 mL) of water after a low-fat (< 30% fat) breakfast. Some examples of low-fat breakfasts are:

- Two slices of white toast with 1 tablespoon of low-fat margarine and 1 tablespoon of jelly and 8 ounces (240 mL) of skim milk (approximately 319 calories and 8.2 g of fat).
- One cup of cereal, 8 ounces (240 mL) of skim milk, one piece of toast with jam (no butter or marmalade), apple juice, and one cup of coffee or tea (2 g fat, 17 g protein, 93 g of carbohydrate, 520 calories).

The medication will be taken in a similar fashion in pediatric patients (< 18 years). ... Pediatric patients on trial will receive tablets according to the dosing table below (Table 5.4). The starting dose is 82 mg/m^2 daily with the same 3 week on, 1 week off schedule as for adult patients. The regorafenib dose will be rounded to the nearest 20 mg and capped at 160 mg as with adult patients. The lowest permissible dose is 20 mg. The minimum body surface area to participate is 0.65m^2 and minimum weight is 15 Kg. (33 lbs.)

Table 5.4 – Pediatric Doses

	BSA > 0.65m 
Dose level 0 (standard starting dose)	82 mg/m  oral daily

For dose modifications, for adult and pediatric patients, refer to tables in Section 6 of the protocol.

Patients, or their guardians, should be instructed to record daily regorafenib or placebo dose on the Study Drug diary which will be provided to them (Appendix C).

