### **8.2 Administration of Study Drugs**

Regorafenib or placebo will be administered as monotherapy during the study. The starting dose of regorafenib on study is 160 mg daily for 3 weeks on, 1 week off. The pediatric starting dose is 82 mg/m^2, rounding to the nearest 20 mg, and capping at 160 mg as with adult patients. One cycle is 28 days. Dose reduction levels are noted elsewhere in this protocol document (see Section 6.1.2).

Four 40 mg regorafenib or four placebo tablets should be taken in the morning with approximately 8 fluid ounces (240 mL) of water after a low-fat (< 30% fat) breakfast. Some examples of low fat breakfasts are:

- Two slices of white toast with 1 tablespoon of low-fat margarine and 1 tablespoon of jelly and 8 ounces (240 mL) of skim milk (approximately 319 calories and 8.2 g of fat)
- One cup of cereal, 8 ounces (240 mL) of skim milk, one piece of toast with jam (no butter or marmalade), apple juice, and one cup of coffee or tea (2 g fat, 17 g protein, 93 g of carbohydrate, 520 calories).

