## 9.2 On Study Evaluation

The following procedures will be performed during the treatment period. Please note that visits may occur  $\pm 2$  days of the scheduled date,  $\pm 3$  days for weeks of bank holidays. Tumor measurements and reimaging may be done  $\pm 7$  days of the anticipated date. Tumor imaging may be performed at other times as clinically indicated. These will be considered non-protocol standard of care scans.

### Cycle 1, Week 1 day 1

- Demographics, interval history
- Concurrent medications
- Physical Exam
- Vitals signs
- Weight
- WHO performance status
- Hematology: complete blood count, platelet count, differential
- Serum Chemistry: electrolytes, chloride, bicarbonate, BUN, creatinine, glucose, ALT, AST, total bilirubin, direct bilirubin, alkaline phosphatase, serum albumin, total protein, calcium, magnesium, phosphorus, lipase, amylase
- For patients for whom there are 14 days or fewer between registration and the start of treatment, the day 1 blood chemistries and hematology may be omitted
- Adverse event evaluation
- Dispense study drug
- Distribute study drug diary, if not already done.

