### **Cycle 2 Week 1, day 1 (Week 5 overall)**

- Demographics, interval history
- Concurrent medications
- Physical Exam
- Vitals signs
- Weight
- WHO performance status
- Hematology: complete blood count, platelet count, differential
- Serum Chemistry: electrolytes, chloride, bicarbonate, BUN, creatinine, glucose, ALT, AST, total bilirubin, direct bilirubin, alkaline phosphatase, serum albumin, total protein, calcium, magnesium, phosphorus, lipase, amylase
- Adverse event evaluation
- Dispense study drug
- Distribute study drug diary
- Collect study drug diary for previous cycle.

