**Grapefruit/grapefruit juice must be avoided while on study**

Your initials/Parent or guardian initials: \_\_\_\_\_

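### The Appendix C diary lets patients take study drug with or without food, whereas sections 5.4 and 8.2 call for morning dosing with or after a low-fat breakfast

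*Combined protocol and SAP*

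**What the plan says.** Section 5.4 (Study drug administration) states that adults start at 160 mg daily, three weeks on and one week off, "taken in the morning with a low-fat meal each day". It then gives the adult tablet instruction, with a volume of water and a limit on the fat content of breakfast, and offers two sample menus. For children it adds: "The medication will be taken in a similar fashion in pediatric patients (< 18 years").

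Section 8.2 (Administration of Study Drugs) repeats that the tablets "should be taken in the morning with approximately 8 fluid ounces (240 mL) of water after a low-fat (< 30% fat) breakfast", with the same menus. It attaches this to four tablets, which is the adult starting dose.

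The note at the foot of the diary in Appendix C reads: "Try to take the study drug daily at the same time, if possible, and consistently with or without food".

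Under section 5.4, patients or guardians "should be instructed to record daily regorafenib or placebo dose on the Study Drug diary which will be provided to them". Section 9.2 has the diary given out at Cycle 1 day 1 ("Distribute study drug diary, if not already done"), again at Cycle 2 day 1 ("Distribute study drug diary"), and at visits from Cycle 3 on.

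**The concern.** The treatment plan fixes the time of day and the kind of meal. The patient's sheet fixes neither; it asks only for a regular time and a regular habit. Someone guided by the sheet could dose outside the plan at every intake while believing that they were following instructions.

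What is at stake is whether the drug is taken as the protocol specifies. Section 8.5 makes the diary the patient's own evidence of compliance. The template, as it appears in the document, has rows for tablets taken, missed doses and side effects, but none for meal or time of intake. A departure on food would therefore not show in it.

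**Working it through.** No arithmetic is involved in the conflict itself. The check is a comparison of texts.

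**Inputs.** Appendix C (diary note); section 5.4 (adult and pediatric intake); section 8.2 (intake repeated); section 9.2 (diary distribution); the synopsis and sections 2.5, 3.1 and 12.2 (who is still to be enrolled).

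**Step 1: does any reading of the note agree with the plan?** The note can mean that a patient should choose fed or fasted and keep to it, or that food does not matter provided the routine is stable. Either way, these habits compare as follows:

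| Habit, kept every day | Diary note | Sections 5.4 and 8.2 |
|---|---|---|
| Morning, after a low-fat breakfast | Complies | Complies |
| Morning, fasted | Complies | Departs |
| Morning, after a high-fat breakfast | Complies | Departs |
| Evening, with a low-fat meal | Complies | Departs |

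The note is looser than the plan. It allows everything the plan asks for, and it also allows three habits that the plan does not.

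**Step 2: does another section reconcile them?** None limits the diary note to a subgroup, and none says that the meal is optional. The tablet sentences in 5.4 and 8.2 are worded as what should be done, but the first statement in 5.4 is unqualified.

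**Step 3: is the diary meant to instruct?** Its main function is to record. It also tells patients to stop after 21 days, which agrees with the schedule in 5.4. It sets an 8-hour limit for late doses, which follows 5.4. It says "Grapefruit/grapefruit juice must be avoided while on study", which agrees with the inhibitor list in Appendix D. The food line is the one dosing instruction among these that does not follow the plan, which suggests a drafting slip more than a deliberate relaxation.

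**Step 4: who is affected from here on?** Section 3.1 marks cohorts A, B and C as fully enrolled as of amendment 5. Cohorts D and E are planned at about 12 each, and 12 + 12 = 24 is the funded total. So at most 24 patients enter through the open cohorts, some of whom may already be on study. Earlier patients still taking the drug would be additional; the documents do not give their number.

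**Step 5: what carries over to children?** Section 5.4 introduces both the starting-dose sentence and the tablet sentence as applying to adults, then says that children take the drug in a similar way without listing the elements. Morning dosing with a low-fat meal is the natural content of that phrase. Whether 240 mL of water and the < 30% fat limit also apply to a child of 5 years and 15 kg, the minimum age and weight for cohort D, is not stated.

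**The case against.** The best case for leaving the text alone has three parts.

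- *The note forbids nothing that the plan requires.* A patient told at the clinic to dose after a low-fat breakfast, who does so daily, satisfies all three texts. This is true. Departure needs a patient who relies on the note instead of, or without, the 5.4 instruction, and the documents do not show that this happens.
- *The diary is a record, and 5.4 and 8.2 govern dosing.* This is largely right and limits the point. It does not remove it, because the same page gives several other instructions that patients are expected to follow.
- *Patients may be told correctly elsewhere.* The consent form and the Operations Manual are not among the documents, and the full label text is not given, so this cannot be settled. If they are told correctly elsewhere, they hold two differing instructions.

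A reader might go further and infer that exposure, efficacy or toxicity has been affected, or that the PFS comparison in cohorts A and B is compromised. The documents do not support that. They contain no food-effect data, they do not show how patients actually dosed, and the template makes no distinction between regorafenib and placebo. A reader might also infer that the whole adult instruction can be printed for every patient once the tablet count is dropped. Section 5.4 does not clearly support that for children.

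**Conclusion.** The diary note and the treatment plan disagree, and the note should be corrected. Confidence in the text comparison is high. Severity is minor: the point concerns one line of a patient-facing template and touches no endpoint, analysis, dose level or safety rule.

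Its forward reach is new patients in cohorts D and E, within a funded total of 24, plus an unstated number of earlier patients still on treatment. The number of doses taken outside the plan cannot be estimated. The conclusion assumes that the Appendix C template is the diary actually in use. It does not depend on what other patient materials say.

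**What to change.** Replace the diary sentence on timing and food with: *Take the study drug in the morning, at about the same time each day, after a low-fat breakfast.* Keep the sentence that follows it, on not repeating a dose after vomiting.

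If the 8 oz (240 mL) water volume and the < 30% fat figure are printed, label them as instructions for adults. This leaves the pediatric line within what section 5.4 supports.

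Re-issue the template to sites for patients entering or still on treatment. The cost is one reworded line and its redistribution, with no change to dosing, endpoints or analysis.

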**Grapefruit/grapefruit juice must be avoided while on study**

Your initials/Parent or guardian initials: \_\_\_\_\_

## **APPENDIX D. Strong CYP3A4 inducers and inhibitors**

### **Listing of strong CYP3A4 inducers to avoid while on study**

Carbamazepine  
Phenobarbital  
Phenytoin  
Rifampin  
St. John's wort

### **Listing of strong CYP3A4 inhibitors to avoid while on study**

Clarithromycin  
Grapefruit juice  
Itraconazole  
Ketoconazole  
Posaconazole  
Telithromycin  
Troleandomycin  
Voriconazole

Source: U.S. Food and Drug Administration: Drug Development and Drug Interactions: Table of Substrates, Inhibitors and Inducers.

<http://www.fda.gov/drugs/developmentapprovalprocess/developmentresources/druginteractionslabeling/ucm093664.htm>

Accessed - 04/04/2017
